4 STUDY ENDPOINTS

4.1 Primary efficacy endpoint(s)

The primary efficacy endpoint of this study is the normalisation of total testosterone levels in $\geq 75\%$ of subjects at Week 24

4.2 Secondary efficacy endpoint(s)

The secondary efficacy endpoints of this study are:

1. Proportion of subjects that have normalisation of total testosterone to Week 24
2. Proportion of subjects that overshoot testosterone (total testosterone above 1000 ng/dL [35 nmol/L]) to Week 24
3. Normalisation of total testosterone in $\geq 90\%$ subjects at Week 24
4. Change of LH and FSH to 24 weeks
5. Population PK analysis of plasma BGS649 concentrations
6. PK analysis of semen BGS649 concentrations.

4.3 Exploratory endpoint(s)

The exploratory endpoints of this study are:

1. Change in oestradiol, inhibins (A and B) levels and DHT
2. Change in testosterone/oestradiol ratio
3. Body composition changes at Week 12 and Week 24
4. Changes in markers of cardiometabolic disease: blood pressure, lipid profile, HbA1c, glucose and insulin, hs-CRP and HOMA-IR and association with change in body composition and testosterone level.
5. Change in markers of bone turnover in those with and without 25-hydroxy vitamin D deficiency
6. Change in total and domain scores on PRO measures (IIEF, PROMIS SexFS: to assess sexual function; BFI, PROMIS Fatigue Short Form, SF-36 - Vitality: to assess energy levels and fatigue; SF-36: to assess general quality of life (QoL); PGI-S: to assess the patients' impression of their current health status) over the 24 week period
7. Association of objective findings of improvement (e.g. testosterone, time in physical activity or sleep and grip strength) and domain scores on PROs
8. Change in physical activity, sleeping pattern and strength measured by wrist worn monitors and grip strength measurement at 12 and 24 weeks and association with body composition (as measured by BMI and waist circumference and impedance) and testosterone level.
9. PK/pharmacodynamic (PD) relationship between BGS649 concentrations and testosterone levels
10. For semen analysis: change in semen parameters throughout the study and association with LH/FSH level
11. Change in bioavailable testosterone

12. Time to first normal testosterone level.

4.4 Safety endpoint(s)

The safety endpoints of this study are:

1. TEAEs/SAEs (from first dose of study drug until 90 days after last treatment dose)
2. Change in PSA during 24 week treatment duration
3. Change in haematocrit during 24 week treatment duration
4. Change in Bone Mineral Density (DEXA scan T-score and density in g/cm²) from Screening and bone turnover biomarkers at 24-weeks from Baseline
5. Change in vital signs and clinical laboratory parameters, ECG
6. Change in physical examination (including general, prostate, breast and oedema of the lower extremities).

5 SAMPLE SIZE AND POWER

The sample size for this study is calculated using exact binomial methods for comparison of a single proportion to a performance goal.

The statistical hypothesis is the proportion of subjects that have normalisation of testosterone at Week 24 within a dose group is greater than the pre-specified performance goal of 75%:

H0: Normalisation \leq 75%

H1: Normalisation $>$ 75%

The calculation assumes a one-sided test conducted at the 2.5% significance level, for which 67 subjects will need to be randomised in each dose group of BGS649.

If the true normalisation rate in a dose group of BGS649 is 90% then the power of the study is 85%.

6 ANALYSIS POPULATIONS

All primary and secondary efficacy endpoints will be analysed using the intention to treat (ITT) and per-protocol (PP) populations.

Safety and tolerability will be analysed using the safety population.

Pharmacokinetic data will be analysed using the PK population.

6.1 Intention-To-Treat population (ITT)

The ITT population includes all subjects who:

1. Are randomised, and
2. Receive at least one dose of study medication, and
3. Provide a Baseline and at least one post-Baseline testosterone value.

Subjects will be analysed according to the treatment to which they were randomised.

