8.6.2 Analysis of primary efficacy endpoint(s)

The Primary Endpoint will be considered to have been met for a dose if $\geq 75\%$ of subjects in the ITT population have normalisation of total testosterone levels (testosterone value is between 300-1000 ng/dL inclusive) at Week 24.

The number and proportion of subjects with normal testosterone levels will be summarised by treatment regimen at each visit using the total testosterone assessed by ICON central lab. The Week 12 total testosterone values assessed by the GLP lab will also be presented. In addition, a P-value for the comparison between each dose will be provided using Fisher's exact test.

Moreover, a bar chart will be presented per treatment regimen for the normalisation of testosterone at each visit showing the percentage of subjects normalised and confidence intervals.

The primary analysis of efficacy will be performed with the ITT population using LOCF imputation. Additionally for exploring the robustness of the intent-to-treat results, a supportive analysis using the PP population using LOCF, ITT population using non-responder analysis (subjects with missing testosterone values will be deemed as not achieving testosterone normalisation) and ITT population using observed cases will be carried out.

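### The set called ITT leaves out dosed men with no post-baseline testosterone value, so even the non-responder analysis cannot count them as failures

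*SAP*

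**What the plan says.** SAP 6.1 sets three conditions for the ITT population: randomised, dosed at least once, and "Provide a Baseline and at least one post-Baseline testosterone value". Protocol 13.3.1 has the same three and adds the words Full Analysis Set to its heading.

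SAP 8.6.2 judges each dose on whether at least 75% of this set is normalised at Week 24. The primary analysis uses LOCF. The supportive analyses are per-protocol with LOCF, a non-responder analysis of the ITT set, and observed cases of the ITT set. In the non-responder analysis, "subjects with missing testosterone values will be deemed as not achieving testosterone normalisation". SAP 6.3 makes the per-protocol set a subset of ITT. SAP 7.2.1 carries forward post-baseline values only.

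A set of all dosed men exists (SAP 6.2), but it serves safety. A randomised set exists (SAP 6.5) for tables and listings. Neither is used for the primary endpoint. SAP 8.3 tabulates the numbers and reasons for exclusion from each set.

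**The concern.** Membership of the primary set depends on a measurement made after randomisation. A man who takes a dose and then leaves before any post-baseline testosterone sample is removed from both numerator and denominator. The non-responder analysis exists to show the result with missing men counted as failures, yet it starts from the same restricted set and cannot reach him.

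The comparison is with a fixed goal, not with placebo, so similar losses in the placebo arm do not offset the effect. Removing a man who would count as a failure changes R/n to R/(n − 1), which is larger whenever R is above zero. Each dose is judged on about 67 men, so a result close to the threshold could turn from fail to pass, and none of the planned robustness analyses would show it.

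**Working it through.** **Inputs from the documents.** 67 men per dose, goal 75%, planned true rate 90%, one-sided 2.5% level, exact binomial method (SAP 5). Success means an observed proportion of at least 75% of the ITT set (SAP 8.6.2).

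**Assumptions.** All 67 randomised men take a dose. The number excluded, k, is 0 to 3; the documents give no figure. True rates of 72% and 75% among all dosed men are illustrations close to the goal; 90% is the planned value.

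**The plan's own figure.** SAP 5 describes a calculation "calculated using exact binomial methods for comparison of a single proportion to a performance goal". With n = 67, the smallest r with P(X ≥ r | 67, 0.75) ≤ 0.025 is 58. The exact level is 1.6%, and P(X ≥ 58 | 67, 0.90) = 87.1%. The stated 85% is therefore reproduced, slightly conservatively; a continuity-corrected normal approximation gives 85.5%.

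**Responders needed under the stated success rule.** c(k) = 0.75 × (67 − k), rounded up:

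- k = 0: 0.75 × 67 = 50.25, so 51
- k = 1: 0.75 × 66 = 49.5, so 50
- k = 2: 0.75 × 65 = 48.75, so 49
- k = 3: 0.75 × 64 = 48, so 48

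**Chance of meeting the rule.** P(X ≥ c(k) | 67 − k, q), with two choices of q:

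- Worst case: every excluded man is a failure. For a true all-dosed rate p, the included men then have rate q = p × 67/(67 − k). At p = 72% this is 73.1%, 74.2% and 75.4% for k = 1, 2 and 3.
- Exclusion unrelated to outcome: q = p.

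| k | Needed | As % of all 67 | p = 72%, worst case | p = 72%, unrelated | p = 75%, worst case |
|---|---|---|---|---|---|
| 0 | 51/67 | 76.1% | 27.4% | 27.4% | 48.1% |
| 1 | 50/66 | 74.6% | 37.1% | 29.9% | 59.5% |
| 2 | 49/65 | 73.1% | 48.0% | 32.5% | 70.5% |
| 3 | 48/64 | 71.6% | 59.4% | 35.3% | 80.1% |

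At p = 90% the chance is about 99.98% or higher in every row, under either assumption.

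**A boundary case.** Suppose 50 men are normalised and one dosed man has no post-baseline sample. The plan computes 50/66 = 75.8%, a pass. Counting him as not normalised gives 50/67 = 74.6%, a fail.

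**If the exact test in SAP 5 were the criterion.** At a true 75%, worst case, the false-positive rate is 1.6% with none excluded, then 3.0%, 5.4% and 4.9% with 1, 2 and 3 excluded. The first is below the nominal 2.5% and the other three are above it.

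**The case against.** **The excluded group is narrow.** Testosterone is drawn on Day 8 and at every later treatment visit (protocol Table 9–1). A man who stops drug should have an EOT visit with the Week 24 assessments within 7 days (protocol 9.3.7). A reader might infer that anyone stopping before Day 8 is lost from the analysis. The documents do not support that, because an EOT sample would keep him in. A missing baseline is also unlikely, since testosterone is drawn twice at screening and baseline is the last pre-dose value (SAP 8.1.5). What remains is mainly men who withdraw consent or are lost to follow-up (protocol 9.3.6 and 9.3.8) before any sample. This stands and limits the size.

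**The probabilities depend on chosen assumptions.** The 72% rate is not in the documents, and it lies near the threshold, where the rule is most sensitive. Nothing shows that every excluded man would have failed. If exclusion is unrelated to outcome, the rise is much smaller, and part of it is rounding: 51/67 is 76.1% while 48/64 is exactly 75%. This stands too, so the worst-case column is an upper illustration and not an expectation.

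**The definition is open and the gap can be traced.** The protocol heading says Full Analysis Set, both documents agree, and exclusions are tabulated by arm. With responder counts reported, a reader could recompute the all-dosed rate. The non-responder analysis also does count as failures all men lost after their first post-baseline sample, so it would be wrong to infer that it ignores dropout in general. This answers any charge of concealment. It does not supply a planned analysis that counts the remaining men.

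**The trial is exploratory.** Protocol 13.5.1 says that all analyses will be considered exploratory. That lowers the stakes, but each dose is still declared to have met the endpoint or not.

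**Conclusion.** The point holds in a limited form. The set called ITT excludes dosed men with no post-baseline testosterone, and no planned primary-endpoint analysis counts them. Under the plan's own non-responder rule the resulting bias has one direction, towards meeting the 75% goal.

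Its size depends on how many such men there are, which the documents do not say and which is probably few. With none, nothing changes. With 1 to 3 of 67 (assumed), the required count drops by one to three responders, and only a result near the boundary changes, from fail to pass. The nominal goal stays at 75% of the analysed set; what falls is the implied share of all dosed men.

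A reader might infer that the exclusion could manufacture success for a dose that performs as planned, or that the 59% figure is a forecast. Neither follows. At the planned 90% a dose passes almost surely with or without the exclusion, and 59% needs three excluded men, all failures, and a true rate of 72%.

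**What to change.** Run the non-responder analysis on all randomised men who took at least one dose, analysed as randomised. Count any missing Week 24 value as not normalised, including for men with no post-baseline value at all. That alone closes the gap.

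Preferably, use the same denominator for the primary LOCF analysis, counting men with no value to carry forward as not normalised. Keep the present set as a sensitivity analysis, labelled full analysis set or modified ITT.

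The cost is wording in SAP 6.1, 7.2.1 and 8.6.2, with an entry in SAP 9 if the primary set departs from the protocol. No new data are needed. The observed normalisation rate may fall slightly.

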6.2 Safety population (Safety)

The safety population includes all subjects who received at least one administration of the study medication.

Subjects will be analysed according to the treatment actually received. Subjects who did not receive the treatment planned by the randomisation will be analysed according to the treatment received.

6.3 Per-Protocol population (PP)

The PP population is a subset of the ITT population and includes all randomised subjects who have been treated according to the protocol and fulfil the following criteria (to be further described in the classification meeting plan):

1. Specific inclusion/exclusion criteria satisfied
2. Absence of relevant protocol violations with respect to factors likely to affect the efficacy of treatment where the nature of protocol violation will be defined before breaking the blind
3. Adequate study medication compliance
4. Adequate measurement of the primary variable.

Subjects will be analysed according to the treatment to which they were randomised.

6.4 PK population

For the nonlinear mixed effects modelling, all subjects who are randomised and received at least one administration of the study medication and have at least 1 quantifiable plasma concentration (either plasma or semen) will be included. Subjects will be analysed according to their randomised treatment.

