To date, BGS649 has also been administered to 21 obese men with HH (8 subjects were assigned to placebo) and was found to be well tolerated without drug discontinuation or drug related serious adverse events (SAEs) (Study CBGS649A2204). This first-in-man study was a 2-part study over 12 weeks (11 treatments); Part 1 was an open-label dose finding study (weekly, individually titrated doses) and Part 2 used a fixed dose regimen (0.3 mg loading dose followed by 10 weekly fixed doses of 0.1 mg). Overall, BGS649 treatment (n=21) resulted in normalisation and maintenance of serum total testosterone, with no evidence of total testosterone peaks above the upper limit of normal (ULN). There were few SAEs reported (only during Part 2 and not considered related to the study drug) and the most commonly reported adverse events (AEs) included spontaneous penile erection and headache. Oestradiol levels were reduced by approximately 25-50% on average and gonadotropin levels (follicle stimulating hormone [FSH] and luteinising hormone [LH]) were increased in subjects treated with BGS649 (no effect observed for subjects on placebo). At the time of the interim analysis of Part 1, new data (Jones et al 2011) indicated that the variances of the homeostatic assessment of insulin resistance (HOMA-IR) were larger than assumed in the original sample size calculations and this (along with the discovery of dosing errors) contributed to the decision for early termination of Part 2 of the study.

A complete review of data obtained to date on BGS649 is presented in the most recent Investigator's Brochure (IB) and Food and Drug Administration (FDA) guidelines have been published on the use of testosterone replacement therapy (Testosterone Replacement Therapy, 2014).

This dose-ranging study aims to demonstrate the efficacy of BGS649 to normalise testosterone (to within normal lab-specific reference range i.e., total testosterone levels 300-1000 ng/dL [10.4-35 nmol/L]) in $\geq 75\%$ of a population of obese male subjects with HH after 24 weeks of double-blind treatment compared to placebo. Study CBGS649A2204 demonstrated that testosterone levels normalised within 2 to 4 weeks of dosing. However, any impact of testosterone levels on the symptoms and signs of hypogonadism is expected to take longer. Therefore, this study evaluates the normalisation of testosterone levels as a primary endpoint, along with key secondary/exploratory endpoints of clinical efficacy after 24 weeks.

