13.3.4 PK Population

For the nonlinear mixed effects modelling, all subjects who received at least one administration and have at least quantifiable concentration will be included.

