3.2 Randomisation and blinding

3.2.1 Randomisation

This is a double-blind randomised study. At Visit 1 (Baseline) all eligible subjects will be randomised via the IRT to one of the four treatment regimens (BGS649 0.1 mg, 0.3 mg, and 1.0 mg and matched placebo) in a 1:1:1:1 ratio. After the interim analysis (see Section 8.8.1.2), if one or more of the BGS649 study arms is discontinued by the DMC, the dosing for that arm(s) will be stopped and no further randomisation to that arm will be performed. The remaining subjects will be randomised into the remaining active arms versus placebo (ineffective or unsafe dose will not continue). The IRT will assign a medication number to the subject, which will be used to link the subject to a treatment regimen and will specify a unique medication number on the label of investigational treatment to be dispensed to the subject.

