8.8.2 PK analyses

Pharmacokinetic samples will be collected as follows:

1. Plasma PK samples will be taken pre-dose and 1h post-dose at Visit 5. At Visit 8 (EOT; Week 24) it will be taken only once.
2. Semen samples for seminal fluid PK will be taken at Visit 8 (EOT)

This plan does not address the PK analyses of BGS649 (Nonlinear mixed effects modelling will be utilised to develop a population PK model for BGS649 plasma concentrations and to develop a PK/PD model linking BGS649 plasma concentrations to changes in testosterone levels). These analyses will be performed by ICON Pharmacokinetics, Pharmacodynamics, Modelling and Simulation Department and will be described in a separate analysis plan. Results from the PK/PD modelling will be reported separately from the CSR.

BGS649 PK plasma concentrations will be summarised for the PK population by descriptive statistics by treatment regimen and time-point, and including the geometric mean and coefficient of variation.

A graphical representation of the PK plasma concentrations distribution using mean plots (mean and SD) will be provided over time per treatment regimen for the PK population. All dose levels will be plotted on the same graph.

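### SAP 6.4 groups the PK population by randomised treatment, so the SAP 8.8.2 concentration tables and plots would show a misdosed man under a dose he did not take

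*SAP*

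**What the plan says.** SAP 6.4 admits to the PK population randomised men who "received at least one administration of the study medication and have at least 1 quantifiable plasma concentration (either plasma or semen) will be included". It does not require that the dose taken was the dose allocated. It ends with the grouping rule: "Subjects will be analysed according to their randomised treatment".

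SAP 8.8.2 uses that population for two descriptive outputs. For the tables: "BGS649 PK plasma concentrations will be summarised for the PK population by descriptive statistics by treatment regimen and time-point". For the mean and SD plots, which put all dose levels on one graph, the display "will be provided over time per treatment regimen for the PK population".

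SAP 6.2 takes the other approach for safety: "Subjects who did not receive the treatment planned by the randomisation will be analysed according to the treatment received".

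Protocol 13.3.4 says only that "all subjects who received at least one administration and have at least quantifiable concentration will be included" and sets no rule on randomised versus received treatment. The grouping rule is therefore the SAP's own. SAP 9, which lists changes from the protocol, mentions only the vitamin D threshold.

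**The concern.** A plasma concentration reflects the dose swallowed. Grouping by allocation protects a randomised comparison, but the 8.8.2 outputs make no such comparison; they describe exposure at each dose. SAP 6.2 already provides for men who did not get their allocated treatment and moves their safety data to what they received. SAP 6.4 does the reverse for the data most directly tied to the dose taken.

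Three things would follow if such a man occurred:

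- His concentrations would enter the summary for the wrong dose.
- If he was allocated to placebo but took active drug, a quantifiable concentration would bring him into the PK population and he would appear under placebo.
- His adverse events and his concentrations would be tabulated under different doses.

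Further determining the PK of BGS649 is a secondary objective (SAP 2.2), and the 8.8.2 outputs are where this SAP itself describes exposure by dose.

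**Working it through.** **Text check**

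1. SAP 6.4 sets grouping by randomised treatment. SAP 8.8.2 names the PK population for both its tables and its plots, and SAP 8.1.1 confirms that PK data use that population. The rule therefore governs those outputs.
2. Nothing overrides it. SAP 8.8.2 has no received-dose provision, SAP 9 does not mention PK, and the Classification Meeting in SAP 6.6 settles violations and exclusions, not regrouping.
3. SAP 6.4 refers to the nonlinear mixed-effects modelling, but SAP 1 and 8.8.2 place that modelling in a separate analysis plan. The effect can be shown only for the descriptive outputs of 8.8.2.

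**Illustration of size**

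The plan gives no figure to reproduce on this point.

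Inputs from the documents:
- Regimens, SAP 3.2.1: "BGS649 0.1 mg, 0.3 mg, and 1.0 mg and matched placebo". The largest active-dose ratio is 1.0/0.1 = 10, and one step up from the lowest dose is 0.3/0.1 = 3.
- Planned arm size, SAP 5: 67.
- Elimination half-life, Protocol 9.2: 21 days.

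Assumptions, not in the documents:
- Concentration is proportional to dose.
- Between 50 and 67 men in the arm contribute a concentration at the time-point (n).
- One man is misdosed, at k times the arm's typical concentration, and the others are at the arm mean.

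Formulas: the arithmetic mean is multiplied by (n − 1 + k)/n and the geometric mean by k^(1/n).

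| Sustained error | n | Arithmetic mean | Geometric mean |
|---|---|---|---|
| 0.1 mg allocated, 1.0 mg taken (k = 10) | 50 | 59/50 = 1.18 | 10^(1/50) = 1.047 |
| | 60 | 69/60 = 1.15 | 10^(1/60) = 1.039 |
| | 67 | 76/67 = 1.13 | 10^(1/67) = 1.035 |
| 0.1 mg allocated, 0.3 mg taken (k = 3) | 50 | 52/50 = 1.04 | 3^(1/50) = 1.022 |
| | 67 | 69/67 = 1.03 | 3^(1/67) = 1.017 |

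**Spread.** Suppose instead that every man varies with a true CV of 40% (an assumption). With k = 10 and n = 67, the mean is 76/67 = 1.134 and the mean square is (66 + 100) × 1.16/67 = 2.874. The SD is √(2.874 − 1.134²) = 1.26, so the CV is 1.26/1.134 = 111%. The plotted SD is affected much more than the mean.

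**One wrong pack.** Assume linear one-compartment kinetics at steady state and a wrong 28-day supply ending at the PK visit. The fraction of the old level remaining is 2^(−28/21) = 0.397. The trough is then 0.397 + 0.603 × 10 = 6.4 times the arm's level, not 10 times. With n = 60 the arithmetic mean is multiplied by (59 + 6.4)/60 = 1.09, against 1.15 for the sustained error. A wrong pack earlier in the study would partly wash out.

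**The case against.** The strongest reply is that the harm is hypothetical and its reach is small. No man in MBGS205 is reported to have received the wrong treatment, and SAP 6.2 is a contingency clause. The outputs affected are descriptive, with no test or decision rule. The geometric mean (SAP 8.8.2) and median (SAP 8.1.3) are also reported and resist one outlier better than the arithmetic mean. Individual listings (SAP 8.1.7) and the summary of exclusions (SAP 8.3) would help a reader trace a mismatch. All of this stands and limits the weight of the point. It does not justify the rule, which makes no difference without an error and gives the wrong label when there is one.

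Four stronger readings are tempting and are not supported:

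- **That dosing errors are a known problem with this product.** Protocol 7.1 says of one earlier study that "this (along with the discovery of dosing errors) contributed to the decision for early termination of Part 2 of the study". That study used individually titrated doses in Part 1 and a loading dose followed by fixed doses in Part 2. The protocol does not say what the errors were or attribute them to the product. In MBGS205, dose changes are not permitted (SAP 3.3).
- **That indistinguishable capsules show a risk of error.** Medication numbers are assigned through the IRT, and each pack's number corresponds to one regimen (Protocol 10.2.1 and 10.2.4). Nothing shows sites combining strengths, and the remaining packaging detail is redacted.
- **That the population PK or PK/PD results are biased.** The modelling plan was not available. Dates and times of drug intake are recorded (Protocol 10.4), as is the time of the last dose before PK sampling (Protocol 11.4), so the models may use actual dosing records.
- **That switching to treatment received has no downside.** SAP 6.2 does not say how to classify a man who took one wrong pack among several. Copying its wording alone would carry that gap into the PK outputs.

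**Conclusion.** The point holds for the 8.8.2 concentration tables and mean plots. As written, SAP 6.4 would label a misdosed man's concentrations with a dose he did not take and separate them from his safety data.

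Its practical size depends on whether such a man exists. With none, nothing changes. One sustained error from the lowest to the highest dose is the extreme active-dose case: 13% to 18% on the arithmetic mean and 3.5% to 4.7% on the geometric mean, given dose-proportional exposure and 50 to 67 sampled men. A sustained one-step error moves the arithmetic mean by about 3% to 4%, and a single wrong pack does less than a sustained error of the same kind. The primary efficacy analysis is not touched. The correction is worth making because the rule does not suit what these outputs describe and is cheap to change.

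**What to change.** Replace the last sentence of SAP 6.4 with: *For concentration summaries and plots, subjects will be analysed according to the treatment actually received.*

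Add a convention for a man misdosed for only part of the study, and settle it before unblinding. Either assign him at each PK time-point by the dose taken before that sample, or list him and leave him out of the summary for the affected time-point. List every man whose randomised and received doses differ, and carry the same rule into the separate PK/PD plan.

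The cost is small. SAP 6.2 already requires treatment received for the safety population, so no new data are needed, and Protocol 13.3.4 sets no grouping rule that the change would contradict. The one real cost is writing the convention for partial misdosing.
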